# List of abbreviations

AE	adverse event
ALQ	above level of quantification
ALP	alkaline phosphatase
ALT	alanine aminotransferase/glutamic pyruvic transaminase/GPT
ANCOVA	analysis of covariance
AST	aspartate aminotransferase/glutamic oxaloacetic transaminase/GOT
ATC	Anatomical Therapeutic Chemical
BLQ	below level of quantification
BMI	Body Mass Index
BSA	body surface area
СНМР	Committee for medicinal products for human use
СМН	Cochran-Mantel-Haenszel
CRP	C-reactive protein
CSA	cyclosporine A
CSR	clinical study report
СТ	computerized tomography
CTCAE	Common Terminology Criteria for Adverse Events
DHP	Data Handling Plan
DLQI	Dermatology Life Quality Index
DNA	Deoxyribo Nucleic Acid
DS&E	Drug Safety & Epidemiology
ECG	Electrocardiogram
eCRF	electronic case report/record form
EQ-5D	EuroQOL 5-Dimension Health Questionnaire®
FAS	full analysis set
FDA	United States Food and Drug Administration
GGT	gamma-glutamyl transferase
HAQ	Health Assessment Questionnaire ©
HAQ-DI	Health Assessment Questionnaire $^{\mathbb{C}}$ – Disability Index
HDL	high density lipoprotein

NovartisConfidentialPage 7RAP Module 39-Apr-2018 (1:15)Secukinumab / AIN457A2302E1

Hgb	Hemoglobin
HRQoL	health-related quality of life
hsCRP	high sensitivity C-reactive protein
IA&R	Integrated Analytics & Reporting
ICH	International Conference on Harmonisation of Technical Requirements for Registration of Pharmaceuticals for Human Use
IDF	International Diabetes Federation
IEC	independent ethics committee
IGA	investigator's global assessment
IGA mod 2011	Novartis Investigator's Global Assessment modified 2011
IIS	Integrated Information Sciences
IRT	interactive response technology
i.v.	intravenous(ly)
IVRS	interactive voice response system
IWRS	interactive web response system
LDL	low density lipoprotein
LLN	Lower Limit of Normal
MACE	Major Adverse Cardiovascular Event
MCMC	Markov Chain Monte Carlo
MedDRA	Medical Dictionary for Regulatory Activities
NMQ	Novartis MedDRA Query
NovDTD	Novartis Drug and Therapy Dictionary
PASI	Psoriasis Area and Severity Index
РВО	Placebo
PD	pharmacodynamic(s)
PD	protocol deviation
PEA	Primary end point analysis
PG	pharmacogenetic(s)
PGIC	Patient Global Impression of Change
PhGA	physician global assessment
PtGA	patient's global assessment
РК	pharmacokinetic(s)

Novartis	Confidential	Page 8
RAP Module 3	9-Apr-2018 (1:15)	Secukinumab / AIN457A2302E1

PsA	psoriatic arthritis
PT	Preferred Term
PUVA	psoralen + UVA treatment
QFT	QuantiFERON TB-Gold test
QTc	QT interval corrected for heart rate
QTcB	QT interval corrected for heart rate using Bazett's formula
QTcF	QT interval corrected for heart rate using Fridericia's formula
REB	research ethics board
RMP	Risk Management Plan
RW	Randomized withdrawal period
SAE	serious adverse event
SDI	Standard Disability Index
SPP	Safety Profiling Plan
s.c.	subcutaneous(ly)
SOC	System Organ Class
ТВ	Tuberculosis
TBL	total bilirubin
TG	Triglycerides
ULN	Upper Limit of Normal
VAS	visual analog scale
WBC	white blood cell

# 1 Statistical methods planned in the protocol and determination of sample size

Data will be analyzed by Novartis using SAS according to the data analysis section 9 of the study protocol which is available in Appendix 16.1.1 of the CSR. Important information is given in the following sections and details are provided, as applicable, in Appendix 16.1.9 of the CSR.

Novartis	Confidential	Page 9
RAP Module 3	9-Apr-2018 (1:15)	Secukinumab / AIN457A2302E1

## 1.1 Statistical and analytical plans

The planned analysis is described in Section 9 (Data Analysis) of the study protocol which is available in Appendix 16.1.1 of the CSR.

This document mainly covers statistical and analytical plans for the final analysis after database lock. The key analyses which conducted previously might be re-run using the final data.

The key secondary analyses during RW period using the final data will be re-run for PASI 75 responders at week 52. The re-run analyses are including summary and analysis of PASI 50/75/90/100 response and IGA 0 or 1 response, loss of PASI 75/IGA 0 or 1 response, time to relapse, and DLQI. Since loss of PASI 75 during randomized withdrawal period will be re-run, the primary endpoint – loss of PASI 75 up to week 68 will not be performed in the final analysis. In addition, a summary of PASI 50/75/90/100 response and IGA 0 or 1 response and IGA 0 or 1 response till week 156 will also be provided using retreatment patients after relapse.

Summary statistics for continuous variables will include N, mean, standard deviation, minimum, lower quartile, median, upper quartile, maximum. Summary statistics for discrete variables will be presented in contingency tables and will include absolute and relative frequencies.

If not otherwise specified, p-values will be presented as two-sided p-values and two-sided confidence intervals will be displayed.

Unless otherwise stated, the level of significance will be set to 5% (two-sided, family-wise type-I-error).

All listings will be presented by treatment sequence.

## 1.1.1 Changes to statistical methods planned in the protocol

Shift tables will be provided for all parameters to compare a subject's baseline laboratory evaluation relative to the most extreme laboratory test value within a treatment period (either RW or treatment period) rather than relative to the visit's observed value.

A listing of immunogenicity data will be provided.

A definition of "rebound-like events" was introduced to capture rebound events that occur at any point after stopping therapy; whereas, the definition of rebound includes only rebound events that occur within 8 weeks of stopping therapy.

For rebound and relapse no imputed data will be used and analyses will be based on observed data only.

Full analysis set included subjects having at least one post baseline efficacy assessment.

## 1.1.2 Footnotes

Footnotes on outputs will be kept to a minimum also for outputs not covered in [Efficacy MAP M7.1] or [Safety MAP M7.1].

Footnotes will generally be provided for

• abbreviations used in the output; abbreviations used on several outputs, e.g. for listings in Appendix 16.2 can be presented on a separate page and do not have to be repeated as footnotes on each listing

Novartis	Confidential	Page 10
RAP Module 3	9-Apr-2018 (1:15)	Secukinumab / AIN457A2302E1

- sorting order of categories, e.g. for sorting within MedDRA (Medical Dictionary for Regulatory Activities) hierarchy levels
- MedDRA version used for reporting of MedDRA coded data

Footnotes will generally NOT be given for

- units displayed on the output
- interpretation of results (e.g. "odds ratio larger 1 favors active treatment")
- information that can be retrieved from the statistical section of the clinical study report (CSR) unless it is not identifiable from the output, e.g.
  - explanation of analysis model used unless results of more than one model are displayed on an output
  - derivations of variables (e.g. BMI will not be explained on a footnote)
- information that will be provided in the clinical study protocol and/or methods section of the CSR (e.g. baseline definition if this is specified in the statistical section of the CSR)

#### 1.2 Subjects and treatments

The following analysis sets will be used for the data analysis.

**Randomized set**: The randomized set will be defined as all subjects who were randomized. Unless otherwise specified, mis-randomized subjects (mis-randomized in IRT) will be excluded from the randomized set. Mis-randomized subjects will be defined as those subjects where IRT contact is made by the site either prematurely or inappropriately prior to confirmation of the subject's final randomization eligibility and double-blind study treatment was not administered to the subject.

PASI 75 non- responders being incorrectly randomized as PASI 75 responders will be analyzed as PASI 75 responders in randomized withdrawal period

**Full analysis set (FAS)**: The FAS will be comprised of all subjects from the randomized set to whom study treatments has been assigned and have at least one post baseline efficacy assessment and on secukinumab at week 52 of core. Following the intent-to-treat principle, subjects will be analyzed according to the treatment assigned to at randomization. If the actual stratum is different to the assigned stratum in IRT, the actual stratum will be used in analyses. PASI 75 non- responders being incorrectly randomized as PASI 75 responders will be analyzed as PASI 75 responders in randomized withdrawal period.

**Safety set**: The safety set includes all subjects who took at least one dose of study treatment during RW period for PASI 75 responders and treatment period for partial responders as well as subjects re-treated after relapse. Subjects will be analyzed according to treatment received.

The treatment received will be set to the treatment randomized. But if a subject has received the wrong treatment during the entire study, the treatment received will be set to this wrong treatment. For those subjects who received erroneously the wrong treatment at least once, an additional listing will be prepared displaying adverse events occurred after the treatment errors.

,,		
Analysis set	PD Population Codes that cause subject to be excluded	Non-PD criteria that cause a subject to be excluded
Randomization set	NA	Mis-randomized subject
FAS (Full Analysis Set)	1, 3	No post baseline efficacy assessment
Safety	2, 3, 6	Not treated in the extension

Table 1-1Subject classification rules

## 1.3 Treatment group definitions

The following treatment labels (Table 1-2, Table 1-3) will be used for re-run tables and final analysis in the order provided below.

#### Table 1-2Treatment groups by subjects group for efficacy analysis

Evaluation of	Analysis Period	Treatment group label (order as listed)	Analysis
Subjects who were PASI 75 responders at Week 52	RW	AIN457 150 mg  AIN457 300 mg  AIN457 150 mg – Placebo  AIN457 300 mg – Placebo 	PASI 50/75/90/100 response and IGA 0 or 1 response Loss of PASI 75/IGA 0 or 1 response Time to relapse DLQI
Subjects who were re-treated after relapse with AIN457 150 mg or 300 mg	Treatment	AIN457 150 mg Placebo - AIN457 150 mg  AIN457 300 mg Placebo - AIN457 300 mg 	PASI 50/75/90/100 response and IGA 0 or 1 response
All subjects	On Treatment Period	AIN457 150 mg stay  AIN457 300 mg stay  All AIN457 150 mg  All AIN457 300 mg  AIN457 150 mg only  AIN457 150 mg - 300 mg  AIN457 300 mg only 	Final analysis

 AIN457 150mg group includes the PASI 75 responders at week 52 who were randomized to AIN150mg at week 52; and the partial responders at week 52 were continued received AIN 150mg from week 52.

 AIN457 300mg group includes the PASI 75 responders who were randomized to AIN300mg at week 52; and the partial responders at week 52 were continued received AIN 300mg from week 52.

Novartis	Confidential	Page 12
RAP Module 3	9-Apr-2018 (1:15)	Secukinumab / AIN457A2302E1

 AIN457 150mg – Placebo group includes the PASI 75 responders who were assigned AIN 457 150mg during core study, and randomized to placebo at week 52.

 AIN457 300mg – Placebo group includes the PASI 75 responders who were assigned AIN 457 300mg during core study, and randomized to placebo at week 52.

 Placebo – AIN457 150mg group includes the subjects who were randomized to placebo at week 52, and relapsed then treated by AIN457 150mg during RW period.

 Placebo – AIN457 300mg group includes the subjects who were randomized to placebo at week 52, and relapsed then treated by AIN457 300mg during RW period.

 AIN457 150 mg stay group includes the subjects who were PASI 75 responders at Week 52 and staying strictly in 150 mg AIN457 treatment from Week 52. The subjects received placebo at Week 52 and switched to AIN457 150 mg will not be included in this treatment group. Subjects up-titrated from AIN457 150 mg to 300 mg during open label period will not be included in this group.

 AIN457 300 mg stay group includes the subjects who were PASI 75 responders at Week 52 staying strictly in 300mg AIN457 treatment from Week 52. The subjects received placebo at Week 52 and switched to AIN457 300 mg will not be included in this treatment group.

 All AIN457 150 mg group includes all the subjects who were assigned to AIN457 150 mg at Week 52, regardless whether they are initial PASI 75 responder or partial responder at Week 52, or who were assigned to placebo at week 52 but relapsed and retreated by AIN457 150 mg during randomized withdrawal period. The subjects who up titrated to 300 mg during the open label period will be included in the efficacy analysis for this treatment group. For the subjects assigned to placebo group at Week 52 and switched to AIN457 150 mg after relapse, the efficacy data after 16 weeks (including 16 weeks) post AIN457 treatment will be included in this group. In addition, the subgroup analysis will be performed for the following two subgroup groups: 1) Subjects who stayed on AIN457 150mg and never were up-titrated; 2) Subjects up-titrated from AIN457 150mg to 300mg during open label period.

All AIN457 300 mg group includes all the subjects who were assigned to AIN457 300 mg at Week 52, regardless whether they are initial PASI 75 responder or partial responder at Week 52, or who were assigned to placebo at week 52 but relapsed and retreated by AIN457 300 mg during randomized withdrawal period. For the subjects assigned to placebo group at Week 52 and switched to AIN457 300 mg after relapse, the efficacy data after 16 weeks post AIN457 treatment will be included in this group. The subjects up titrated during the open label period will not be included in this group.

AIN457 150 mg only group is from 'ALL AIN457 150 mg' group and includes the subjects who were PASI 75 responders or partial responder at Week 52 and staying strictly in 150mg AIN457 treatment from Week 52. The subjects received placebo at Week 52 and switched to AIN457 150 mg will not be included in this treatment group. Subjects up-titrated from AIN457 150mg to 300mg during open label period will not be included in this group.

 AIN457 150 mg - 300 mg group is from 'ALL AIN457 150 mg' group and includes the subjects who started AIN457 150 mg from Week 52 and up-titrated from AIN457 150mg to 300mg during open label period.

 AIN457 300 mg only group is from 'ALL AIN457 300 mg' group and includes the subjects who were PASI 75 responders or partial responder at Week 52 and staying strictly in 300mg AIN457 treatment from Week 52. The subjects received placebo at Week 52 and switched to AIN457 300 mg will not be included in this treatment group.

Evaluation of	Analysis Period	Treatment group label (order as listed)	Comment on treatment group definition	
Table/Figure	Entire stud Period, Follow-up Period	
 
y Any AIN 457 150 mg Any AIN 457 300 mg Any AIN 457 dose AIN 457 150 mg – Placebo AIN 457 300 mg – Placebo
 
2 Any AIN 457 150 mg Any AIN 457 300 mg Any AIN 457 dose
 
	Same as in Table 1-1 Same as in Table 1-1	

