#### Table 1-3 Treatment groups by subjects group for safety analysis

 Any AIN457 150 mg group includes all the subjects who have ever received at least one dose of AIN457 150 mg from Week 52 to Week 256 (Week 260 EOT no dose), regardless whether they are initial PASI 75 responder or partial responder at Week 52. For the subjects assigned to placebo group at Week 52 and switched to AIN457 150 mg after relapse or started AIN457 150 mg during open label period, the safety data during and after 1st AIN457 dose will be included in this group. For subjects starting with 150 mg AIN457 dose and switched to 300 mg AIN457, the period used the low dose will be counted for the 'Any AIN457 150mg' group.

 Any AIN457 300 mg group includes all the subjects who have ever received at least one dose of AIN457 300 mg from Week 52 to Week256 (Week 260 EOT no dose), regardless whether they are initial PASI 75 responder or partial responder at Week 52. For the subjects assigned to placebo group at Week 52 and switched to AIN457 300 mg after relapse or started AIN457 300 mg during open label period, the safety data during and after 1st AIN457 dose will be included in this group. For subjects starting with 150 mg AIN457 dose and switched to 300 mg AIN457 at any time, the period after switching to the high dose will be included in the 'Any AIN457 300 mg' group.

 AIN457 150mg – Placebo group includes the PASI 75 responders who were assigned AIN 457 150mg during core study, and randomized to placebo at week 52. Only data for subjects received placebo period were included in safety analysis.

 AIN457 300mg – Placebo group includes the PASI 75 responders who were assigned AIN 457 300mg during core study, and randomized to placebo at week 52. Only data for subjects received placebo period were included in safety analysis.

So, for re-run efficacy analysis the data will be analyzed for RW period. Regarding retreatment patients after relapse, the data till week 156 will be presented. For data analysis till week 156, the following treatment groups will be reported

#### • Subjects who were PASI 75 responders at Week 52

AIN457 150 mg AIN457 300 mg AIN457 150mg - Placebo AIN457300mg - Placebo

• Subjects who were re-treated after relapse with secukinumab 150 mg or 300 mg

AIN457 150 mg AIN457 300 mg Placebo - AIN457 150 mg Placebo - AIN457 300 mg

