For final analysis, the following treatment groups will be reported for the on treatment period.

AIN457 150 mg stay AIN457 300 mg stay All AIN457 150 mg All AIN457 300 mg AIN457 150 mg only AIN457 150 mg - 300 mg AIN457 300 mg only

The following study periods will be considered for analysis:

- Screening period (before Randomization in extension)
- **Randomized** withdrawal (RW) period for subjects who were PASI 75 responders at Week 52- the duration of RW period for each subject is different i.e., starting from Week 52 until the subject experiences the first full relapse for efficacy analyses and until the subjects reinitiating the secukinumab after first full relapse for safety analyses. RW period is not fixed for all the subjects but varies for subject to subject based on occurrence of relapse. Subjects not experiencing the relapse will end their RW period at Week 156.
- **Treatment** period for subjects with relapse (for efficacy analyses it is starting from the visit in RW period at which a subject experiences first full relapse to Week 156. Safety analysis will not be re-run for subjects with relapse).
- **Treatment** period for subjects with partial response (Week 52 to Week 156)
- **Open label** period for subjects who were continued in the study and were unblinded at Week 156. The first open label dose were given at the site at Week 156. Subjects previously randomized to receive 150 mg secukinumab may continue with 150 mg secukinumab open label or may switch to 300 mg s.c. at the discretion of the investigator. Subjects previously randomized to 300 mg secukinumab continued with 300 mg secukinumab open label. Placebo subjects who entered the open label period were given once weekly s.c. injections of secukinumab for 4 consecutive weeks and then s.c. injections every 4 weeks. Any subject starting on secukinumab 150 mg may continue on 150 mg every 4 weeks or switch to 300 mg at Week 156 or any other regular site visit if the investigator decided the subject would benefit from the higher dose. The Week 244 visit was the last scheduled visit at which the subjects were allowed to switch to 300 mg dose. Decreasing the dose from 300 mg to 150 mg was not allowed.
- Follow-up (FU) period (for all subjects)\*: treatment free period (Week 264 to Week 268).

Novartis	Confidential	Page 15
RAP Module 3	9-Apr-2018 (1:15)	Secukinumab / AIN457A2302E1

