Week 132	132	561	Day 548-575
Week 136	136	589	Day 576-603
Week 140	140	617	Day 604-631
Week 144	144	645	Day 632-659
Week 148	148	673	Day 660-687
Week 152	152	701	Day 688-715
Week 156	156	729	Day 716-743
Week 168	168	813	Day 744-855
Week 180	180	897	Day 856-939
Week 192	192	981	Day 940-1023
Week 208	208	1093	Day 1024-1149
Week 220	220	1177	Day 1150-1219
Week 232	232	1261	Day 1220-1303
Week 244	244	1345	Day 1304-1387
Week 260	260	1457	Day 1388-1471
Week 264	264	1485	Day 1472-1499
Week 268	268	1513	Day 1500-1527
3 WK after last study drug admin.**			Week 264 visit

Novartis	Confidential	Page 21
RAP Module 3	9-Apr-2018 (1:15)	Secukinumab / AIN457A2302E1

12 WK after last study		Week 268 visit
drug admin.**		

\* Baseline measurement before the first drug administration for safety assessments and before the randomization for efficacy assessments. The days are counted since the first dose of study treatment in extension for safety assessments, and the days are counted since the date of randomization in extension for efficacy assessments.

\*\* 8/12 WK after last study drug administration will be used for re-bound analysis.

For parameters which are not collected at every visit (e.g. DLQI, EQ-5D, HAQ-DI), visit windows defined in Table 1-5 will be combined. For example, if a parameter is measured at Week 64 and Week 76 only, Week 64 visit window will extend from Day 2 to Day 99 (combining Week 56 to Week 64 visit windows), Week 76 will extend from Day 100 to Day 183 (combining Week 68 to Week 76). If more than one assessment falls into the interval, the rules defined in section 1.5.5 below are applied.

Assessments from treatment period will not be considered for RW period. Assessments from RW period will not be considered for treatment period. Assessments from RW and treatment period may be considered for follow-up period.

Assessments from RW/treatment period will not be considered for open label period. Assessments from open label period will not be considered for RW/treatment period.

The 'by visit' safety summaries for the 'whole treatment period' will be reported as per the analysis visits relative to Week 52 as defined in Table 1-5.

Of note, for subjects who discontinue in RW period, i.e. not moving into treatment period, efficacy measurements taken in follow-up period would still be considered for RW period as specified in Section 1.9.4.1.

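### SAP Table 1-2, footnotes 1 and 2, put partial responders, who were never randomised against placebo, into the active groups of the randomised-withdrawal analyses

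*SAP*

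**What the plan says.** SAP 1.3 makes the labels in Table 1-2 operative: "The following treatment labels (Table 1-2, Table 1-3) will be used for re-run tables and final analysis in the order provided below".

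The first row of Table 1-2 covers Week 52 PASI 75 responders in the RW period. Footnotes 1 and 2 appear only on that row's two active labels. Footnote 1 takes the PASI 75 responders randomised to 150 mg and then adds a second set: "and the partial responders at week 52 were continued received AIN 150mg from week 52". Footnote 2 does the same for 300 mg. The comparator is narrower. The footnote 3 definition reads "Placebo group includes the PASI 75 responders who were assigned AIN 457 150mg during core study, and randomized to placebo at week 52", and footnote 4 matches it for 300 mg.

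Elsewhere the SAP describes a different population:

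- SAP 1.1: "The key secondary analyses during RW period using the final data will be re-run for PASI 75 responders at week 52".
- SAP 1.3, list of groups up to Week 156: these same labels stand under "Subjects who were PASI 75 responders at Week 52".
- SAP 1.3, study periods: RW is defined for PASI 75 responders, and partial responders have their own treatment period from Week 52 to Week 156.
- SAP 1.5.4: "Assessments from treatment period will not be considered for RW period".
- SAP 1.9.4.1 says that partial responders do not enter RW, and the RW part of 1.9.6 is headed for PASI 75 responders randomised to RW.
- SAP Table 1-14 restricts the risk sets for loss of PASI 75 and loss of IGA 0 or 1 to PASI 75 responders who enter RW.

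The protocol agrees. Sections 3.1 and 3.2 re-randomise only PASI 75 responders. Section 5.3 gives partial responders a randomisation number, but it is linked only to the active dose they already receive.

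**The concern.** The clause enlarges the active side only. It adds subjects who, by definition, lack PASI 75 at Week 52 and who never had a chance of assignment to placebo. A comparison built on these groups is no longer randomised.

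The analysis set does not prevent this. Partial responders have randomisation numbers, and nothing in the SAP 1.2 definition of the full analysis set removes them. Model adjustment does not repair it either: the logistic model in SAP 1.9.6 adjusts for region, body weight stratum and core baseline PASI, not for response at Week 52.

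Three outputs are exposed:

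- the by-visit PASI 50/75/90/100 and IGA 0 or 1 comparisons with placebo (Cochran-Mantel-Haenszel and logistic, SAP 1.9.6);
- the RW DLQI summaries (SAP 1.9.10);
- RW time to relapse, because Table 1-14 gives a relapse risk set for the follow-up period only.

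The by-visit comparisons start at Week 52, the randomisation visit, so the groups would already differ at time zero.

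**Working it through.** **The plan's own figure.** Protocol 9.7 and SAP 1.11 claim more than 90% power with about 400 subjects per dose, randomised 2:1, with 10% against 23% losing PASI 75 and one-sided alpha of 2.5%.

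- Hazard ratio = ln(0.90)/ln(0.77) = 0.403.
- Expected events = 400 × (2/3 × 0.10 + 1/3 × 0.23) = 57.3.
- Power (Schoenfeld) = Φ(√(57.3 × 2/9) × |ln 0.403| − 1.96) = 90.0%. Freedman's formula gives 94.3%. With 414 subjects the two give 91.0% and 95.0%.

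The claim reproduces. It rests on 276 active and 138 placebo subjects per dose, all randomised PASI 75 responders. The footnotes would give a different active group.

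**Inputs for the size of the effect.** PASI 50 rate 0.95 (Protocol 4). PASI 75 rate p = 0.65 (Protocol 9.7, stated for 150 mg). Randomisation 2:1. The documents give no PASI 75 rate for 300 mg, so 0.75 and 0.85 are assumed to show a range.

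**Share of partial responders in the pooled active group.** s = (0.95 − p) / [(0.95 − p) + 2p/3]

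| p | s | Week 52 PASI 75, pooled active (1 − s) | Week 52 PASI 75, placebo |
|---|---|---|---|
| 0.65 | 0.300/0.733 = 40.9% | 59.1% | 100% |
| 0.75 | 0.200/0.700 = 28.6% | 71.4% | 100% |
| 0.85 | 0.100/0.667 = 15.0% | 85.0% | 100% |

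The share does not depend on the total enrolled. Among randomised subjects the Week 52 comparison is 100% against 100% by definition, apart from any PASI 75 non-responders randomised in error (SAP 1.2). The Week 52 figures need no assumption about later response.

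**Partial responders per dose.** N × (0.95 − p)/0.95/2, assuming an equal split between doses. For N = 1,146 (the number randomised, Protocol Amendment 2) this gives 181, 121 and 60. For the planned N = 1,220 it gives 193, 128 and 64. As a cross-check from the planned 414 per dose, (1,220 − 828)/2 = 196, and 196/(196 + 276) = 41.5%.

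**Later visits.** If a is the response rate in randomised active subjects and r the rate in partial responders, the pooled rate is (1 − s)a + sr. Pooling lowers the active rate by s(a − r), which is 4.1, 2.9 or 1.5 points for each 10-point gap.

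As an illustration only, take 90% and 77% (one minus the planned cumulative losses) as a rough proxy for Week 68 response on active and placebo. These are not planned by-visit rates. The pooled active rate equals placebo when r = (0.77 − 0.90(1 − s))/s, that is 58%, 45% or 3%. Below that value the contrast reverses. Above it, and below 90%, the contrast is diluted. The documents do not give r.

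**The case against.** The strongest reply is that the pooling would not happen. The row of Table 1-2 is itself limited to PASI 75 responders in RW. SAP 1.1, 1.3, 1.5.4 and 1.9.6 all point the same way, and if treatment-period assessments are barred from RW, partial responders contribute no post-baseline data to an RW table. The SAP's list of changes from the protocol (1.1.1) declares no pooling, and protocol section 9 lists the two populations separately. This stands as evidence that the clause is probably a drafting error, and it makes the effect conditional. It does not remove the problem: these footnotes are the only written definition of the RW active labels, and SAP 1.3 says to use the labels.

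A second reply is that the clause may serve the row for subjects re-treated after relapse, which reuses the two active labels without footnotes, while SAP 1.5.4.1 mentions relapse in partial responders. This fails. SAP 1.3 starts that treatment period at a relapse within RW, and SAP 1.9.4 places the re-treated subjects among the Week 52 PASI 75 responders. Nor does the all-subjects row need the clause: footnotes 9 and 10 already include subjects "regardless whether they are initial PASI 75 responder or partial responder at Week 52", and footnotes 11 and 13 name partial responders too.

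A third reply is partly right. SAP 1.9.4 handles other time-to-event analyses in the same way as loss of PASI 75, and protocol 9.5.1 treats relapse by analogy, so the PASI 75 responder risk set may carry over to time to relapse. That output is less clearly exposed than the by-visit comparisons.

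The size beyond Week 52 also remains open, because it depends on a response rate that is not given.

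**Conclusion.** The concern holds. Footnotes 1 and 2 state a group rule that contradicts their own row, the rest of the SAP and the protocol, and the error falls on the active side alone. The other passages identify the intended population: PASI 75 responders randomised into RW.

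If the footnotes were applied literally, about 41% of the active group would be non-randomised at the planning rates (29% or 15% at assumed PASI 75 rates of 75% or 85%). The Week 52 comparison would show a 41-point deficit on active (29 or 15 points) created by the group definition alone. These figures rest on planning rates, not observed ones. Whether later contrasts would be diluted or reversed cannot be settled from the documents.

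The Week 68 primary analysis is untouched and is not re-run under this SAP. Table 1-14 protects loss of PASI 75 and loss of IGA 0 or 1. The exposed outputs are secondary re-runs outside the testing strategy. The point should be fixed, but it does not threaten the main conclusion.

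**What to change.** Delete the partial-responder clause from footnotes 1 and 2 of SAP Table 1-2, or move it to a separate label used only in the all-subjects row. Add one sentence to SAP 1.3: the RW response-by-visit, DLQI and time-to-relapse outputs include only subjects randomised into RW.

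The cost is two footnotes and one sentence, with no new data. Programs that already follow SAP 1.9.6 need no change; any whose group filter follows the footnotes must be corrected. The stated power does not change, because the groups return to the planned 276 against 138 per dose.
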